7.5.1 Primary Endpoint

- **Successful revascularization (final mTICI \geq 2b), as determined by Core Lab**

The number and percentage of subjects achieving a final mTICI score \geq 2b will be summarized using mITT analysis set. A two-sided 95% CI using the normal approximation method will be constructed around the percentage.

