## 10.5.4. Primary and Secondary Endpoint Analyses

### 10.5.4.1. Primary Endpoint Analysis

The analysis of the performance endpoints will be conducted in the mITT population.

- **Successful revascularization (final mTICI  $\geq 2b$ )**

The number and percentage of subjects achieving a final mTICI score  $\geq 2b$ , as determined by Imaging Core Lab, will be summarized. Two-sided 95% confidence intervals using the normal approximation method will be constructed around the percentage.

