#### 10.5.4.2.1. Secondary Effectiveness Endpoints

- **Successful Revascularization (final mTICI  $\geq 2b$ ) without rescue therapy, as determined by Core Lab**

The number and percentage of subjects achieving a final mTICI score  $\geq 2b$  as determined by Imaging Core Lab without use of rescue therapy, will be summarized. Two-sided exact 95% confidence intervals will be constructed around the percentage.

- **Complete revascularization (final mTICI  $\geq 2c$ ), as determined by Core Lab**

The number and percentage of subjects achieving a final mTICI score  $\geq 2c$ , as determined by Imaging Core Lab, will be summarized. Two-sided exact 95% confidence intervals will be constructed around the percentage.

- **First Pass Effect (mTICI  $\geq 2c$  without rescue), as determined by Core Lab**

The number and percentage of subjects with complete angiographic reperfusion defined as mTICI score of  $\geq 2c$  after first pass with the EMBOVACTM Aspiration Catheter as determined by Imaging Core Lab without use of rescue therapy, will be summarized. Two-sided exact 95% confidence intervals will be constructed around the percentage.

- **Modified First Pass Effect (mTICI  $\geq 2b$ ), as determined by Core Lab**

The number and percentage of subjects with complete angiographic reperfusion defined as mTICI score of  $\geq 2b$  after first pass with the EMBOVACTM Aspiration Catheter as determined by Imaging Core Lab, will be summarized. Two-sided exact 95% confidence intervals will be constructed around the percentage.

- **Time to recanalization (Time from arterial puncture to complete recanalization mTICI  $\geq 2b$ ), as determined by Core Lab**  
The procedure time from arterial puncture to complete recanalization (achievement of the first mTICI score of at least 2b or greater), as determined by Imaging Core Lab, will be summarized. If a subject was not able to achieve an mTICI score of 2b or greater, the time from arterial puncture to visualization of the final angiogram will be summarized.
- **Modified Rankin Scale (mRS) 0-2 at 90 days**

The number and percentage of subjects achieving mRS 0-2 at 90 days will be summarized. Subjects with missing mRS scores due to all-cause mortality are considered to have an mRS score of 6 in the analysis, all other data will be summarized using observed data. Two-sided exact 95% confidence intervals will be constructed around the percentage.

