7.3	Demographic and Baseline Characteristics.....	7
7.4	Procedural Characteristics.....	7
7.5	Primary and Secondary Endpoints.....	7
7.5.1	Primary Endpoint.....	8
7.5.2	Secondary Endpoints	8
7.5.2.1	Secondary Effectiveness Endpoints.....	8
7.5.2.2	Secondary Safety Endpoints.....	9
7.6	Health Economic Endpoints.....	10
7.7	Clot Analysis	10
7.8	Analyses of Adverse Events (AEs).....	11
7.9	Plans for Interim Analyses	12
7.10	Handling of Missing Data	12
7.11	Sensitivity Analyses.....	12
7.12	Subgroup Analysis.....	12
7.13	Additional Analyses.....	13
7.14	Changes from Planned Analyses	13

1 Study Design

This is a prospective, multi-center, single-arm, post-market clinical follow-up study that will enroll approximately 100 subjects at approximately 10 sites primarily in Europe, with clot collection for follow-on histopathological analysis. Subjects will be included in the study for a period of 3 months after the procedure, including follow up visits at 24 hours, 7 days (or discharge) and 90 days after the procedure.

2 Treatment Assignment

This is a single arm study and all enrolled subjects are intended to be treated with the study device, the EMBOVAC Aspiration Catheter.

3 Interval Windows

Study reports will be summarized using analysis visits as defined below.

- 24 Hours post-procedure (-12 to +48 hours)
- 7-Day/Discharge (-1 to +7 days)
- 90-day follow-up (± 15 days)

The study schedule is to be adhered to as closely as possible for all subjects. Data will be summarized by scheduled visit. Measurements outside the analysis windows will be considered as missing in the analysis. In the case of repeated measurements taken at the same visit, the most recent measurement with non-missing values will be used unless specified otherwise.

4 Levels of Significance

No hypothesis tests are planned in the study. All confidence intervals will be reported at a two-sided 95% confidence level. These confidence intervals will not be used for statistical inferences, but for clinical reference purpose and are intended to convey precision in the estimates.

5 Analysis Sets

The following analysis sets are defined in the study:

- **Modified Intent-to-Treat (mITT) Analysis Set**

The mITT analysis set will consist of enrolled subjects who have received treatment (at least one pass; a pass being defined as use of aspiration followed by evaluation of revascularization with angiography) with the study device.

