A subject is considered enrolled in this study once the physician confirms subject meets all eligibility criteria and the subject signs the informed consent.

The mITT analysis set will be used to analyze effectiveness endpoints.

- **Safety Analysis Set**

The safety analysis set will consist of all enrolled subjects in whom the treatment was attempted, defined by the advancement of the EMBOVAC Aspiration Catheter inside of the subject.

The safety analysis set will be used to analyze safety endpoints.

6 Sample Size Justification

There is no statistical power calculation and no hypothesis tests for this post-market study. 100 subjects are deemed sufficient to characterize the performance of EMBOVAC Aspiration Catheter.

Approximately 100 subjects will be enrolled. With an enrolled sample size of 100 and an attrition rate of no more than 5%, the precision (margin of error) for the primary endpoint is anticipated to be around 8.0% based on 2-sided 95% confidence intervals, where the primary endpoint rate is estimated to be 80%.

$$\text{Margin of error} \approx 1.96 \times SE = 1.96 \times \sqrt{\frac{p(1-p)}{n}} = 1.96 \times \sqrt{\frac{0.8 \times (1-0.8)}{95}} = 8.0\%$$

where SE denotes the standard error and p denotes the proportion of subjects who achieve the primary endpoint.

7 Analyses to be Conducted

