7.5 Primary and Secondary Endpoints

Modified Thrombolysis in Cerebrovascular Infarction (mTICI) scores will be summarized using the assessments from the independent core lab. Missing mTICI scores will be excluded from the analysis.

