7.5.2 Secondary Endpoints

Secondary effectiveness endpoints will be analyzed in the mITT analysis set and secondary safety endpoints will be analyzed in the safety analysis set. Two-sided 95% CIs using binomial exact method will be constructed if required by the endpoint. Missing data will be excluded from the analysis unless instructed otherwise.

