7.5.2.2 Secondary Safety Endpoints

Device-related SAEs and all-cause mortality, Kaplan-Meier analysis (using product limit estimates) will be applied. Kaplan-Meier event rate and its associated two-sided 95% CIs using log-log transformation will be reported, the estimate of standard error will be computed using Greenwood's formula.

- **Devices related serious adverse events (SAEs) within 90 days of follow up as determined by an independent Clinical Events Committee**

Kaplan-Meier analysis will be performed to analyze the device related SAE rate within 90 days. Device related SAEs are considered as events; where the event date is the date of first event. Subjects without events will be censored at the date of last contact. The event rate at 90 days with associated 95% CIs will be provided. Device related SAEs beyond 90 days will be listed.

- **sICH at 24h post procedure specified according to the Heidelberg Bleeding Classification (HBC) as determined by an independent Clinical Events Committee**

sICH at 24 hours post procedure as specified by HBC will be assessed. The number and percentage of subjects with events will be summarized with CIs.

- **NIHSS at 24h post procedure**

The observed NIHSS total score at 24 hours post-procedure and changes from the baseline score will be summarized.

- **90 Day All-Cause Mortality**

Kaplan-Meier analysis will be performed to analyze all-cause mortality within 90 days. All-cause mortality is considered as the event; where the event date is the date of mortality. Subjects without events will be censored at the date of last contact. The event rate at 90 days with associated 95% CIs will be provided. Deaths beyond the 90 days will be listed.

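### Minor: the primary rate has a normal-approximation interval that is slightly too favourable at its lower limit, and the Kaplan-Meier interval for device-related SAEs has no rule for zero events

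*SAP*

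**What the plan says.** **Primary rate.** SAP 7.5.1 states: "A two-sided 95% CI using the normal approximation method will be constructed around the percentage". Protocol 10.5.4.1 says the same: "Two-sided 95% confidence intervals using the normal approximation method will be constructed around the percentage". The sample-size text matches. In SAP 6, "the precision (margin of error) for the primary endpoint is anticipated to be around 8.0% based on 2-sided 95% confidence intervals", computed at 80% with 95 evaluable subjects; protocol 10.4 and the protocol summary carry the same formula. Under SAP 7.5, "Missing mTICI scores will be excluded from the analysis", so the denominator depends on how many core-lab readings are available.

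**Secondary effectiveness rates.** Protocol 10.5.4.2.1 uses a different method: "Two-sided exact 95% confidence intervals will be constructed around the percentage". SAP 7.5.2 has: "Two-sided 95% CIs using binomial exact method will be constructed if required by the endpoint".

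**Device-related SAEs.** SAP 7.5.2.2 assigns Kaplan-Meier to this endpoint and to all-cause mortality: "Kaplan-Meier event rate and its associated two-sided 95% CIs using log-log transformation will be reported", with Greenwood's standard error. It promises a 90-day interval without exception.

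**Role of the intervals.** SAP 4 says that they are not for inference and "are intended to convey precision in the estimates".

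**The concern.** With no hypothesis test, the interval is the only statement of uncertainty that accompanies each rate. Two things follow.

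First, the most important rate gets the less accurate interval, and no reason is given. The first secondary endpoint is the primary endpoint with rescue counted as failure. If no subject needed rescue, the two counts would be the same but would carry different intervals. The normal interval's misses also fall mostly on one side: too often its lower limit, which a reader takes as the worst plausible performance, is above the truth.

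Second, if no device-related SAE is seen, the specified method returns no interval. A zero rate would then be reported without an upper bound, or with one chosen after the data are known.

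**Working it through.** **Inputs.** Two-sided 95%, z = 1.96 (SAP 4). Planned rate 80%; 100 enrolled and up to 5% attrition, so n = 95 (SAP 6). I used n = 90 to 100 because missing core-lab readings are excluded; the lower end is an assumption. True rates of 75-85% bracket the plan. Rates of 85-95% are assumed, as a case above plan.

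**The plan's own figure.** 1.96 × √(0.8 × 0.2 / 95) = 8.04%, stated as 8.0%. It reproduces.

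**Coverage.** For each n and each of 2,001 equally spaced true rates, I summed the binomial probabilities of the counts whose interval contains the true rate, and of those whose lower limit exceeds it, then averaged.

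| True rates | Method | Coverage | Lower limit above truth |
|---|---|---|---|
| 75-85% | Normal | 94.0% | 4.4% |
| 75-85% | Wilson | 95.1% | 2.0% |
| 75-85% | Exact | 96.3% | 1.8% |
| 85-95% | Normal | 92.5% | 6.4% |
| 85-95% | Wilson | 95.2% | 1.6% |
| 85-95% | Exact | about 96.7% | 1.5% |

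At exactly n = 95 and a true 80%, the normal interval covers 94.0% with a lower miss of 4.2%.

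**Limits at n = 95.**

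| Count | Normal | Wilson | Exact |
|---|---|---|---|
| 76 (80.0%) | 71.96-88.04% | 70.86-86.81% | 70.54-87.51% |
| 86 (90.5%) | 84.64-96.42% | 82.97-94.94% | 82.78-95.58% |
| 93 (97.9%) | 95.01-100.78% | 92.65-99.42% | 92.60-99.74% |

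At 76/95, Wilson lies 80.0 − 70.9 = 9.1 points below the estimate and 86.8 − 80.0 = 6.8 above. Exact lies 9.5 below and 7.5 above. At 93/95 the normal upper limit passes 100%.

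**Zero events.** The log-log limits for survival S are S raised to the power exp(±1.96 × SE / (S × |ln S|)). With no event, S = 1, Greenwood's SE is 0 and ln S = 0, so the exponent contains 0/0 and no limit exists. With one event in 100 and no censoring, S = 0.99 and SE = 0.99 × √(1/(100 × 99)) = 0.00995, giving an event rate of 1% with limits 0.14% and 6.89%. The failure is therefore confined to zero events.

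**How often this would happen.** The documents give no expected rate. For an assumed true rate r, the chance of zero events is (1 − r)^n:

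| r | n = 100 | n = 95 |
|---|---|---|
| 0.5% | 61% | 62% |
| 1% | 37% | 38% |
| 2% | 13% | 15% |
| 3% | 4.8% | 5.5% |
| 5% | 0.6% | 0.8% |

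**Exact upper limit with zero events,** 1 − 0.025^(1/n): 3.6% for 0/100, 3.8% for 0/95, 4.5% for 0/80.

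**The case against.** On the primary rate, the documents agree with each other and with the margin formula, no performance goal exists, and the SAP disclaims inference. At the planned rate, exact is further from 95% than the normal interval (96.3% against 94.0%), and the larger deficit needs true rates above plan. All of that stands. It keeps the point minor, and it means that exact cannot be justified by closer overall coverage. What remains is the lopsided miss at the lower limit, which Wilson and exact both remove.

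On zero events, SAP 7.5.2 covers safety endpoints too and could be read as making the exact method the default. But that wording applies only where an endpoint requires it, and 7.5.2.2 then assigns Kaplan-Meier to this endpoint, so the fallback is inferred and not stated. The count itself would not be lost: protocol 10.5.4.2.2 requires number and percentage without promising an interval, and SAP 7.8 tabulates SAEs and device-related AEs. Protocol 3.2.3 also counts events where the device cannot be ruled out, which makes zero less likely.

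Three stronger readings do not hold. A reader might infer that protocol and SAP conflict on the primary interval, or that the 8.0% is wrong; neither is so. A reader might take every secondary rate to have an exact interval; in the SAP, device-related SAEs and mortality use Kaplan-Meier. And a reader might think that Kaplan-Meier is unsuitable for this endpoint; it fails only at zero events.

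**Conclusion.** Both parts hold, and both are minor.

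1. The normal interval is a consistent, prespecified choice that slightly overstates precision on the favourable side. Around the planned rate, coverage is 94.0% and the lower limit is too high 4.4% of the time instead of 2.5%. At assumed true rates of 85-95% these become 92.5% and 6.4%. The figures rest on binomial sampling and 90 to 100 evaluable subjects.
2. The interval promised for device-related SAEs does not exist if no event occurs, and no fallback is stated. That the method fails is a matter of algebra. How likely this is depends wholly on a rate that the documents do not give.

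No hypothesis, performance goal or stopping decision depends on either interval.

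**What to change.** **Primary rate (protocol 10.5.4.1, SAP 7.5.1).** Specify the Wilson interval, or the exact method already used for the secondary effectiveness rates. Wilson is closest to 95% but leaves the primary and secondary methods different. Exact gives one method for all the effectiveness rates but is conservative. In the protocol summary, protocol 10.4 and SAP 6, give expected precision as limits and not as one symmetric margin: at 76/95, Wilson 70.9-86.8% or exact 70.5-87.5%.

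Cost: one software option and a few sentences. The primary lower limit falls by 1.1 points (Wilson) or 1.4 (exact) at 76/95, and by 84.64 − 82.97 = 1.7 or 84.64 − 82.78 = 1.9 at 86/95.

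**Device-related SAEs (SAP 7.5.2.2).** Keep Kaplan-Meier and add: *If no device-related SAE occurs, 0/n will be reported with an exact binomial 95% CI, where n is the safety analysis set, together with the number of subjects without follow-up to 90 days.* This keeps the denominator that the plan assigns to safety endpoints.

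Cost: one sentence. This n counts subjects with incomplete follow-up as event-free, so the bound is slightly optimistic. A version limited to subjects with complete follow-up may be shown as support: if 20 of 100 had incomplete follow-up (assumed), its upper limit would be 4.5% instead of 3.6%. It should not replace the main one, because it drops treated subjects who died or left early.

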7.5.2 Secondary Endpoints

Secondary effectiveness endpoints will be analyzed in the mITT analysis set and secondary safety endpoints will be analyzed in the safety analysis set. Two-sided 95% CIs using binomial exact method will be constructed if required by the endpoint. Missing data will be excluded from the analysis unless instructed otherwise.

7.5.2.1 Secondary Effectiveness Endpoints

- **Successful Revascularization (final mTICI \geq 2b) without rescue therapy, as determined by Core Lab**

The number and percentage of subjects achieving a final mTICI score \geq 2b without rescue therapy will be summarized with CIs. Subjects who received rescue will be considered as failures and included into the denominator of the rate.

- **Complete revascularization (final mTICI \geq 2c), as determined by Core Lab**

The number and percentage of subjects achieving a final mTICI score \geq 2c will be summarized with CIs.

- **First Pass Effect (mTICI \geq 2c without rescue), as determined by Core Lab**

The number and percentage of subjects with an mTICI score \geq 2c after first pass with the EMBOVAC Aspiration Catheter without rescue therapy will be summarized with CIs. Subjects who received rescue during the first pass will be considered as failures and included into the denominator of the rate.

Subjects with a missing mTICI score at pass one from the imaging core lab, will be imputed with the final (end of procedure) mTICI score from the imaging core lab if the total number of passes equal to one and no post mechanical thrombectomy interventions and no intra-arterial thrombolytic agent were performed post first pass one.

- **Modified First Pass Effect (mTICI \geq 2b), as determined by Core Lab**

The number and percentage of subjects with an mTICI score of \geq 2b after first pass with the EMBOVAC Aspiration Catheter, regardless of rescue therapy, will be summarized with CIs.

- Subjects with a missing mTICI score at pass one from the imaging core lab, will be imputed with the final (end of procedure) mTICI score from the imaging core lab if

the total number of passes equal to one and no post mechanical thrombectomy interventions and no intra-arterial thrombolytic agent were performed post first pass.

- **Time to recanalization (Time from arterial puncture to complete recanalization mTICI $\geq 2b$), as determined by Core Lab**

The procedure time, in minutes, from arterial puncture to complete recanalization (achievement of the first mTICI score $\geq 2b$) will be summarized. If a subject was not able to achieve an mTICI score of 2b or greater, the time from arterial puncture to visualization of the final angiogram will be used. Time of arterial puncture, visualization of final angiogram, imaging time per pass will all be based on site reported data; mTICI reading will be based on the core lab.

- **Modified Rankin Scale (mRS) 0-2 at 90 days**

The number and percentage of subjects achieving mRS 0-2 at 90 days (75 days or above) will be summarized with CIs. Subjects with missing mRS scores due to all-cause mortality are considered to have an mRS score of 6 in the analysis, subjects with missing mRS scores due to reasons other than all-cause mortality will be excluded. Subjects with mRS scores outside or didn't reach the 90-day window, due to reasons other than mortality, will be listed together with their mTICI scores at end of procedure.

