##### 3.2.2. Secondary Effectiveness Endpoints

1. **Successful Revascularization (final mTICI  $\geq$  2b) without rescue therapy, as determined by Core Lab** – Successful achievement of the endpoint is defined as achieving a final mTICI score of 2b or greater in the target vessel as determined by the independent Imaging Core Lab without use of rescue therapy.
2. **Complete Revascularization (final mTICI  $\geq$  2c), as determined by Core Lab** – Successful achievement of the endpoint is defined as achieving a final mTICI score of 2c or greater in the target vessel as determined by the independent Imaging Core Lab.
3. **First Pass Effect (mTICI  $\geq$  2c without rescue), as determined by Core Lab** – Subjects with complete angiographic reperfusion defined as mTICI of 2c or greater after the first pass with the EMBOVACTM Aspiration Catheter as determined by the independent Imaging Core Lab without use of rescue therapy.
4. **Modified First Pass Effect (mTICI  $\geq$  2b), as determined by Core Lab** – Subjects with complete angiographic reperfusion defined as mTICI of 2b or greater after the first pass with the EMBOVACTM Aspiration Catheter as determined by the independent Imaging Core Lab.

5. **Time to recanalization (Time from arterial puncture to complete recanalization mTICI  $\geq$  2b), as determined by Core Lab** – as the time from arterial puncture to achievement of the first mTICI score of 2b or greater, or visualization of final angiographic result if an mTICI score of 2b or greater is not achieved, as determined by the independent Imaging Core Lab.
6. **Modified Rankin Scale (mRS) of 0 - 2 at 90 days** - Must be performed by a qualified independent evaluator. Whenever possible, mRS should be recorded at the follow-up clinic visit. If not possible, then a telephone assessment may be used.

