### 3.3. Rescue Therapy

In order to provide an evaluation of the device, rescue therapy should not be used prior to completion of the first three passes with the EMBOVAC™ Aspiration Catheter.

Rescue therapy is defined as:

- Any change in frontline device therapy to remove the target occlusion in a vessel at least 2mm in size.
- Use of intra cranial stenting during the procedure
- Use of an intra-arterial thrombolytic agent during the procedure (e.g., tissue plasminogen activator, urokinase, prourokinase)

Progression in therapy to address thrombus/occlusion that is no longer appropriate for treatment with EMBOVAC™ (e.g., use of another device to remove distal occlusion in a vessel smaller than 2mm) will be considered an appropriate evolution in the standard of care and NOT considered rescue therapy.

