## 7.3. Procedure

The clinical decision to use the EMBOVAC™ Aspiration Catheter, as well as the revascularization procedure are independent (regardless) of the research. Physicians should follow the most current EMBOVAC™ Aspiration Catheter Instructions for Use (IFU) at all times with regards to the device compatibility, preparation and the recommended retrieval procedure. The research procedures are limited to the collection of data. Data will be collected before, during, and after use of the EMBOVAC™ Aspiration Catheter.

During the procedure, the following data will be collected:

- Total number of passes: A pass is defined as use of aspiration followed by evaluation of revascularization with angiography.
- Procedural angiography – The following will be recorded by the clinical site:
  - mTICI score per each attempted pass
  - Procedure Time defined as time from arterial puncture to complete recanalization (first mTICI  $\geq$  2b)
- Thrombectomy techniques and devices utilized per pass
- Additional interventions performed (if applicable)
- Record any reportable AEs per this protocol which occur during the procedure and up to the time of the 24hour examination.
- Clot collection per pass: this study aims to collect the clot from all subjects enrolled. However, in consideration of the urgent nature of stroke treatment, if the clot cannot be collected in a study procedure, it will not be considered a protocol deviation.

Once subject eligibility has been confirmed, the subject can be enrolled in the study.

**A subject is considered enrolled in this study once the physician confirms the subject meets all eligibility criteria and the subject or their legal representative has provided informed consent.**

A subject will not meet inclusion criteria and must not be enrolled if the EMBOVACTM Aspiration Catheter is not used for the first 3 clot removal passes for the target intracranial occlusion (unless use of another device is needed to remove clot in a distal vessel  $<2$ mm in diameter).

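### The SAP's First Pass Effect rule fails a subject only for rescue given in pass 1, a limit that the protocol's definition does not contain and SAP 7.14 does not log

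*SAP*

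**What the plan says.** Protocol 3.2.2 defines First Pass Effect as mTICI 2c or better after the first EMBOVAC pass, "as determined by the independent Imaging Core Lab without use of rescue therapy". Protocol 10.5.4.2.1 repeats the condition for the analysis: "as determined by Imaging Core Lab without use of rescue therapy, will be summarized". Neither place says over what period rescue is counted.

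SAP 7.5.2.1 opens the endpoint in matching terms, counting subjects at 2c or better "after first pass with the EMBOVAC Aspiration Catheter without rescue therapy will be summarized with CIs". The next sentence is the operative failure rule: "Subjects who received rescue during the first pass will be considered as failures and included into the denominator of the rate".

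Two neighbouring endpoints in the same SAP section handle rescue differently:

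- Final mTICI 2b or better without rescue: "Subjects who received rescue will be considered as failures and included into the denominator of the rate", with no limit on timing.
- Modified First Pass Effect: "regardless of rescue therapy, will be summarized with CIs".

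On when rescue can occur, Protocol 3.3 says that "rescue therapy should not be used prior to completion of the first three passes with the EMBOVAC™ Aspiration Catheter". Protocol 7.3 says that a subject must not be enrolled if EMBOVAC "is not used for the first 3 clot removal passes for the target intracranial occlusion", apart from the exception for clot in a distal vessel under 2 mm. Protocol 3.3 lists three kinds of rescue. Intracranial stenting and intra-arterial thrombolytic are each tied to the procedure as a whole. A change of frontline device on the target carries no time reference.

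**The concern.** The SAP's failure rule adds a time limit that the protocol clause lacks, and SAP 7.14, which lists changes from planned analyses, does not mention it. The limit falls in the part of the procedure where the protocol makes rescue least likely. The rule therefore has few subjects to act on, and the endpoint comes close to a plain count of 2c or better after pass 1 while keeping a label that says rescue was absent.

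The subjects at issue are those scored 2c or better after pass 1 who later received, for example, an intracranial stent or an intra-arterial thrombolytic. The failure rule allows them to be counted as successes without rescue. The SAP's lead sentence, taken alone, would not. Two programmers working from this text could therefore report different rates from the same data.

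**Working it through.** **Texts side by side**

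| Endpoint | Protocol 3.2.2 | SAP 7.5.2.1 failure rule |
|---|---|---|
| Final mTICI 2b or better, no rescue | no use of rescue, no time limit | any rescue is a failure |
| First Pass Effect, 2c or better | no use of rescue, no time limit | only rescue in pass 1 is a failure |
| Modified First Pass Effect, 2b or better | no rescue condition | rescue ignored |

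The protocol uses the same condition in the first two rows. In the first row it has to cover the whole procedure, because the score is the final one. The SAP keeps that scope in the first row and narrows it in the second.

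**The plan's own figure.** The only design figure is the margin of error for the primary endpoint (Protocol 10.4, SAP 6), with p = 0.80 and n = 95 (100 enrolled, at most 5% attrition):

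1.96 × √(0.8 × 0.2 / 95) = 8.04%, which agrees with the stated 8.0%.

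This figure does not depend on the First Pass Effect rule.

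**Effect per affected subject.** Let x be the number of successes under the SAP rule and k the number of those who had rescue after pass 1. With the same denominator n under both rules:

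- SAP rule: x/n
- Rescue counted over the whole procedure: (x − k)/n
- Difference: k/n, which is never negative; at n = 95 it is 1/95 = 1.05 percentage points per subject.

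**Illustration.** The documents give neither a First Pass Effect rate nor k, so both are assumptions here. Take x = 38 and n = 95, with exact binomial 95% intervals as SAP 7.5.2 specifies:

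| k | Rate | 95% CI |
|---|---|---|
| 0 (SAP rule) | 38/95 = 40.0% | 30.1 to 50.6 |
| 1 | 37/95 = 38.9% | 29.1 to 49.5 |
| 3 | 35/95 = 36.8% | 27.2 to 47.4 |
| 5 | 33/95 = 34.7% | 25.3 to 45.2 |

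The difference k/n does not depend on x. Starting from 28/95 (29.5%) or 48/95 (50.5%), the drop is again 1.1, 3.2 and 5.3 points for k = 1, 3 and 5.

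**Who is affected.** A subject below 2c after pass 1 fails under either rule, whatever happens later. Only a subject at 2c or better after pass 1 (at least 90% reperfusion on the scale in Protocol Table 3) who then receives rescue changes status.

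**The case against.** The strongest reply is that First Pass Effect describes the state of the vessel after one pass. The rescue condition can then be read as qualifying that state, and the SAP merely makes the reading explicit. The protocol is silent on the window; it does not say that rescue counts at any time. This reading is possible. The use of the same condition for the final score and the per-procedure definition of two kinds of rescue favour the wider reading, but do not settle it. For that reason the fix leaves room for a declared pass-1 window.

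Four stronger readings are tempting, and the documents do not support them:

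- *The SAP states that later rescue counts as success.* It does not. Its lead sentence still requires absence of rescue, so the SAP is internally inconsistent rather than explicit.
- *First Pass Effect contradicts the final-score endpoint.* A subject can meet an endpoint scored after pass 1 and fail one scored at the end of the procedure. Different results at different time points are not in themselves a contradiction.
- *The rescue condition is empty.* Protocol 3.3 discourages early rescue but does not forbid it, and the enrolment bar in Protocol 7.3 concerns the device used, not a thrombolytic or a stent. Rescue in pass 1 can still occur in an enrolled subject. The rule acts on few subjects, not on none.
- *The endpoint exists to show that one pass was enough.* No section says so. Under the protocol's own condition, a subject at 2c after pass 1 who then has further EMBOVAC passes without rescue remains a success.

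It is also fair to say that the effect per subject is small beside an interval about 20 points wide, and that SAP 7.13 already tabulates mTICI by pass.

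**Conclusion.** The point holds as an unlogged narrowing in the SAP and an inconsistency between its lead sentence and its failure rule. Measured against the protocol clause read over the procedure, the SAP rule can only leave the rate unchanged or raise it, by 1.05 points per affected subject. That size assumes 95 analysed subjects and the same denominator under both rules; at 100 it would be 1/100 = 1.00 point. The direction rests on the whole-procedure reading. If a pass-1 window was intended, there is no upward bias, but the definition is still not the same in the two documents.

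The number of affected subjects cannot be derived from the documents and is probably small, since it requires near-complete reperfusion after pass 1 followed by rescue. The endpoint is secondary and descriptive, no hypothesis is tested, and the primary endpoint and its precision are untouched. Severity is minor.

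**What to change.** Align the failure rule in SAP 7.5.2.1 with the protocol. Suggested wording: *Subjects who received rescue therapy, as defined in Protocol 3.3, at any time during the index procedure are counted as failures for First Pass Effect and remain in the denominator.* Add one supporting row giving the rate of 2c or better after pass 1 regardless of later rescue. SAP 7.13 already summarises mTICI by pass, so that row is largely available.

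If the sponsor intends rescue to count only in pass 1, it should state that window in Protocol 3.2.2 and 10.5.4.2.1 and in the SAP's lead sentence, and log it in SAP 7.14.

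The cost is one SAP sentence and one table row. No new data are needed: Protocol 7.3 already collects devices per pass and additional interventions, and the SAP's imputation rule for a missing pass-1 score already uses interventions and thrombolytic given after that pass. The downside is that the reported rate may be slightly lower.
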